N-acetylcysteine (NAC), a safe and well-tolerated medication, supplements endogenous GSH levels by providing cells with the rate-limiting component of GSH synthesis (i.e., cysteine) in exchange for glutamate. Though research has long demonstrated that NAC increases peripheral GSH levels, investigation of the effects of NAC on brain GSH levels has been limited to a few studies in people with Parkinson's disease and early psychosis, which found that NAC significantly increased cortical GSH levels. Based on the hypothesis that NAC treats residual BD impairments by increasing brain GSH levels, a number of randomized clinical trials (RCTs) of adjunctive NAC for BD have been conducted over the past 10-15 years. A recent meta-analysis of these RCTs found a statistically-significant, moderate effect of NAC on reducing depressive symptoms; secondary data analyses further demonstrated that NAC significantly increased working memory performance. Despite this support for NAC as a promising adjunct treatment for BD, the (GSH-mediated) mechanistic hypothesis on which these studies have been predicated has never been tested in BD individuals, and a plausible (glutamate-mediated) alternative hypothesis exists.

It is against this background that the proposed randomized, double-blind, placebo-controlled, crossover MRI study aims to measure and experimentally-increase GSH levels in dACC (selected among candidate brain regions given its central role in guiding motivated human behavior), using NAC (3g/day), in BD participants. Twelve BD participants will complete two, 2-week experimental conditions (NAC, placebo) in a randomized order, separated by a 2-week washout. The study will evaluate the following hypotheses:

Primary: NAC treatment will significantly increase dACC GSH levels, relative to placebo, in BD individuals.

Exploratory: 1) NAC treatment may significantly reduce dACC glutamate levels, relative to placebo, in BD individuals. **2)** Associations of NAC-related changes in dACC GSH and glutamate levels with peripheral biomarkers of oxidative stress (plasma GSH, s-glutathionylation), mood, and cognition will be explored.

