2) The proposed study will be the first to investigate brain GSH levels in BD individuals using optimal, j-difference, ¹H-MRS methods (Sanaei, 2017); specifically, a TE-optimized version of the MEGA-PRESS sequence demonstrated to provide excellent SNR and test-retest reliability of dACC GSH levels (Prisciandaro, 2020).

A. RESEARCH PLAN

C.1. Overview. The proposed randomized, placebo-controlled, double-blind, crossover MRI study will evaluate the effects of 3g/day of NAC on dACC GSH levels in BD. BD participants will complete two, 14-day experimental conditions (NAC, placebo) in a randomized order, separated by a 14-day washout period. Each condition will consist of an in-person study visit for assessment and dispensing of medication (Day 1) and an MRI (Day 14). See *Figure 3* below for a study design schematic.

Figure 3. Study Design

C.2. Participants. Twelve healthy, men and women age 18-60 with BD will be enrolled across 10-months (i.e., following a 1-month study-initiation, and followed by a 1-month closeout, period). The

study team has successfully recruited and retained BD participants for >10 years via clinical referral (e.g., MUSC Institute of Psychiatry, Charleston and Dorchester Mental Health Center) and advertising (e.g., radio, Facebook, Craigslist), 97% of whom have agreed to be re-contacted. This past year, we screened out ≥10 people/month who were diagnosed with BD, but failed to meet entry SUD criteria, who could have been available for this study. We anticipate approximately 35% of recruited participants will be minorities.

C.2.a. Recruitment. We will focus recruitment efforts for the proposed study on the following primary sources:

1) *Medical University of South Carolina (MUSC)*

- a. Inpatient - Over the past 10+ years, we have forged strong ties with the clinical enterprise of the MUSC Institute of Psychiatry. Study staff visit MUSC residents and attending physicians across 4 inpatient units, 3x/week. If the inpatient treatment team believes a patient may be eligible and interested in participating in the current study, they will approach the patient and gain approval for the research study staff to speak with the patient. If they agree, the patient will then be asked questions by study staff to screen for eligibility.

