C.4.a. Sample Size Determination. In the only published investigation of chronic NAC dosing on brain GSH levels in a psychiatric sample, a 23% increase in medial prefrontal GSH was found in (2.7g/day) NAC-treated participants with early psychosis, in contrast to the 4.6% decrease found in placebo-treated participants (Conus, 2018). Our test-retest investigation of TE-optimized MEGA-PRESS for Figure 2. Sample (a) dACC voxel placement (top panel), and (b) fitted GSH spectra from 80ms (left) and 120ms (right) TE MEGA-PRESS acquisitions. GSH in 11 HC demonstrated excellent stability in within-subject dACC GSH levels (*M* Coefficient of Variation = 7.25%). Using variance/covariance estimates from Prisciandaro (2020), we calculated statistical power across a range of potential magnitude between-treatment changes in dACC GSH levels. With *n*=10 study

completers ($n=12$ enrolled with an estimated dropout rate of 15-20%), the proposed study would have >80% power to detect the 23% NAC-induced increase in GSH levels reported in Conus (2018) ($\alpha=0.05$, two-tailed; IBM SPSS v27).

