C.4.b. Data Analysis. Linear mixed effects models will be used to assess the effect of NAC on dACC GSH levels (*Hypothesis 1*). Models will be re-estimated with dACC glutamate levels entered in place of GSH levels (*Exploratory Hypothesis 1*). We predict that NAC will *increase* GSH levels, but *decrease* glutamate levels, relative to placebo. *Exploratory Hypothesis 2* will be evaluated by adding the following variables, setwise, as interacting time-varying covariates to the *Hypothesis 1* linear model: i) plasma GSH levels, extent of s-glutathionylated proteins, ii) YMRS, MADRS scores, and iii) NIH Toolbox-Cognition Battery scores. Models will contain the main effect of treatment (NAC vs. placebo), period (scan 1 vs. scan 2), and sequence (NAC 1st vs. placebo 1st) to ensure the crossover design and washout were successful. Although mood-stabilizing medications have not been associated with GSH levels (Das, 2019), we will evaluate them, along with other baseline variables that may be associated with OS (age, sex, smoking status; Keaney, 2003), as moderators across analyses to facilitate rigor and reproducibility and inform future studies. Within-voxel tissue content will be evaluated as a covariate across models. We will employ previously successful methods to minimize attrition. Where missing data cannot be avoided, mixed models yield valid inferences assuming data are missing at random.

C.5. DISCUSSION

C.5.a. Overview. Despite available efficacious treatments, BD remains a leading driver of global disease burden. Convergent evidence supports ACC GSH levels as a promising interventional target, and NAC as a candidate adjunctive treatment to increase brain GSH levels, in BD individuals. The proposed randomized, placebo-controlled, double-blind, crossover MRI study aims to increase dACC GSH levels using NAC (3g/day) in individuals with BD and to evaluate medication-related, GSH- and glutamate-mediated changes in mood, cognition, and plasma biomarkers of OS, in individuals with BD. The study will be conducted by a BD research team with a successful 10+ year record of collaboration, using imaging methods optimized by the study team. Results may support the development of increasingly-targeted medications designed to fight excessive OS through increasing brain GSH levels that would clinically benefit individuals with BD.

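### Exploratory Hypothesis 2 puts whole sets of interacting markers into a model with 8 within-person degrees of freedom, and the number of cognition scores is not stated

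*Combined protocol and SAP*

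**What the plan says.** Section C.4.a plans on 10 completers out of 12 "enrolled with an estimated dropout rate of 15-20" percent. The Specific Aims speak of all twelve: "Twelve BD participants will complete two, 2-week experimental conditions (NAC, placebo) in a randomized order". Section C.1 gives one scan per condition: "Each condition will consist of an in-person study visit for assessment and dispensing of medication (Day 1) and an MRI (Day 14"). Table 2 lists spectroscopy at Visits 3 and 5 only, so each completer contributes two GSH values and there is no baseline scan.

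The base model is set out in C.4.b: "Models will contain the main effect of treatment (NAC vs. placebo), period (scan 1 vs. scan 2), and sequence (NAC 1st vs. placebo 1st"). Exploratory Hypothesis 2 "will be evaluated by adding the following variables, setwise, as interacting time-varying covariates to the" Hypothesis 1 model. The first two sets are "i) plasma GSH levels, extent of s-glutathionylated proteins, ii) YMRS, MADRS scores"; the third is "iii) NIH Toolbox-Cognition Battery scores".

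The plan does not say how many cognition scores enter or whether a composite is meant. It does not name what the covariates interact with, how within-person and between-person marker effects are kept apart, or which df method is used. The only power statement, in C.4.a, is for the primary treatment contrast.

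**The concern.** The Specific Aims ask how changes in brain GSH and glutamate under NAC go with peripheral biomarkers, mood and cognition. Only within-person variation answers that. In a two-period crossover with one scan per period, each completer supplies exactly one within-person GSH difference, so there are about ten such differences for everything the model must estimate. Setwise entry puts all markers of a set into one model, and the interactions add further terms. The parameter count therefore approaches the number of differences quickly.

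This is the plan's only analysis linking brain GSH to plasma markers, mood and cognition. If the within-person information runs out, mixed-model software may still print coefficients. Those would rest partly or wholly on differences between people, and a reader could take them as evidence about mechanism.

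**Working it through.** **The plan's own figures.** 12 x 0.85 = 10.2 and 12 x 0.80 = 9.6, so about 10 completers is consistent. Taking the 7.25% CV in C.4.a as the within-person SD, the SD of a within-person difference is sqrt(2) x 7.25 = 10.25%. Power for a 23% increase with 10 completers is then above 99.9% (two-sided 0.05, 8 or 9 df), so the stated figure of more than 80% holds as a lower bound. No corresponding figure exists for Exploratory Hypothesis 2.

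**Within-person df.** Sequence is constant within a person and costs nothing here. Treatment and period cost one each: 10 - 2 = 8 (or 12 - 2 = 10).

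**Cost of m markers.** Assume the interaction is with treatment. Each marker then adds two within-person columns, so residual df = n - 2 - 2m. Matrix-rank checks of the design confirm the following.

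| Markers in the model | n = 10 | n = 12 |
|---|---|---|
| 1 | 6 df | 8 df |
| 2 (sets i and ii) | 4 df | 6 df |
| 3 | 2 df | 4 df |
| 4 | 0 df, saturated | 2 df |
| 5 | not estimable (12 coefficients, rank 10) | 0 df, saturated |
| 6 or more | not estimable | not estimable |

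Saturated means that the coefficients can be solved but no error estimate is left.

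**Other interaction partners.** Period or sequence gives the same count. If the markers interacted only with each other, a set would add m + m(m-1)/2 terms: 3 for two markers (5 df left at n = 10), 6 for three, and 10 for four (more than the 8 available).

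**Precision.** Assume a CV of 7.25% and half of each marker's variance within person. The second figure is not in the documents. With total marker SD 1, the within-person marker difference then has SD sqrt(2 x 0.5) = 1. An approximate half-width for an average slope is t x 10.25 / sqrt(n - c), where c is the number of other within-person columns.

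- One marker, no interaction, n = 10: c = 2, 7 df, 2.365 x 10.25 / sqrt(8) = 8.6. Simulated median 8.4.
- Two interacting markers, n = 10: c = 5, 4 df, 2.776 x 10.25 / sqrt(5) = 12.7. Simulated median 12.6.
- One marker, no interaction, n = 12: 9 df, 2.262 x 10.25 / sqrt(10) = 7.3. Simulated median 7.2.
- Two interacting markers, n = 12: 6 df, 2.447 x 10.25 / sqrt(7) = 9.5. Simulated median 9.4.

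Units are GSH percentage points per marker SD. The ratio at n = 10 is 12.6 / 8.4 = 1.5.

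**Range for the unsourced assumption.** Half-widths scale roughly with 1 / sqrt(within-person share). At a 25% share, multiply by sqrt(0.50/0.25) = 1.41: 12.6 becomes 17.8 and 8.4 becomes 11.9. At 75%, multiply by sqrt(0.50/0.75) = 0.82: about 10.3 and 6.9. The ratio of 1.5 barely moves.

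**Overfitting of a two-marker set.** With pure noise, the added terms are expected to explain 4/8 = 0.50 of the remaining within-person variance. A marker needs a partial correlation of 2.776 / sqrt(2.776^2 + 4) = 0.81 to reach p < 0.05. With one marker and no interaction the figure is 2.365 / sqrt(2.365^2 + 7) = 0.67.

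**The case against.** The analysis is labelled exploratory, no power or confirmatory claim rests on it, and the primary comparison does not depend on it. That stands, and it limits the consequence. It does not make the model suitable for a question about change.

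Several stronger readings are tempting, and the documents do not support them.

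- A reader might infer that the cognition set cannot be estimated at all. That depends on a number the plan does not give. One composite leaves 6 df and two scores leave 4. Even four scores at n = 10 saturate the model and do not make it rank deficient.
- A reader might infer that the two-per-marker count holds for any interaction. It fails for a two-marker set whose markers interact only with each other: 5 df remain, not 4.
- A reader might set the interval for three markers against the planned 23% effect. Like for like, the average-slope half-width is about 23.4 at n = 10. However, it falls below 23 if 75% of marker variance is within person or if all 12 complete. A slope per marker SD and a treatment effect are also different quantities.
- A reader might infer that chance findings will dominate. Few df widen intervals; with proper df they do not raise the error rate per test. Ten independent coefficient tests would give 1 - 0.95^10 = 40% for at least one false positive, but one joint test per set would give 1 - 0.95^3 = 14%. The plan does not say which is meant.

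Another fair objection is that a mixed model uses between-person information as well, so its total df are larger (8 fixed effects on 20 observations for a two-marker set). That is true, but the extra information does not bear on change under NAC.

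**Conclusion.** The point holds as a matter of parameter count and under-specification. At the planned 10 completers, sets i and ii each consume half of the 8 within-person df if the markers interact with treatment. The interval for an average slope is then about 1.5 times as wide as with one marker and no interaction (12.6 against 8.4 points; 9.4 against 7.2 with 12 completers). The widths rest on the 7.25% CV from healthy controls and on an assumed 50% within-person share; the df count rests on neither.

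For cognition, the conclusion is conditional on the unstated number of scores. At n = 10, three leave 2 df, four leave no error estimate, and five or more are not estimable within person. Any mixed-model output for five or more would draw on between-person differences and not on changes under NAC. Choosing the scores after seeing the data would decide whether the model can be fitted within person at all, which is a reason to settle it now. Any tissue-content covariate that varies between scans would reduce the df further.

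This is worth correcting before analysis, and it leaves the NAC-versus-placebo comparison of GSH untouched.

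**What to change.** Reword the Exploratory Hypothesis 2 sentence in C.4.b as follows.

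- Enter one marker per model, split into the person's mean over the two scans and the deviation from it. Interpret the slope on the deviation. A single uncentred marker in a random-intercept model would still blend within-person and between-person associations.
- For set iii, name one summary cognition score in advance.
- Omit the marker-by-treatment term, or report it one marker at a time as a secondary description.
- State a small-sample df method.
- Report each slope with its 95% interval as descriptive, without significance claims.

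Without the interaction, each slope keeps 8 - 1 = 7 within-person df at 10 completers and 10 - 1 = 9 at 12. The person mean is a between-person term and costs none of these.

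The change needs no new data, visits or participants. It gives up mutual adjustment of markers within a set and estimates for individual cognition subtests. It also leaves little or no information on whether associations differ between NAC and placebo.

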psychotic symptoms (CAPE-42), suicidal ideation (CHRT; Trivedi, 2008), anxiety (STAI), anger (STAXI), and insomnia (ISI), will be evaluated. Participants will complete the STOP-IT and Delay Discounting computer tasks. Participants will take their final medication dose in front of staff, 1 hour before MRI, to ensure compliance. Unused study medications will be returned for pill counts. Participants who smoke will be allowed to have their last cigarette immediately prior to their final medication dose. Participants will provide blood and urine samples to test for gabapentin levels, riboflavin, and OS biomarkers. Total scan time is 60 min in a Siemens 3.0T

Prisma (32-ch head coil) with actively shielded magnet and high-performance gradients. Participants will discontinue study medication following each MRI. To minimize

[figure not shown]

Figure 4. Sample (a) dACC voxel placement (top panel), and (b) fitted GSH spectra from 80ms (left) and 120ms (right) TE MEGA-PRESS acquisitions.

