14. Has taken NAC in the last month or experienced adverse effects/allergic reaction from it at any time
15. Significant claustrophobia and/or past negative experiences with MRI
16. Presence of non-MRI safe materials in the body (e.g., ferrous metal implants, pacemaker)

b. Source of Materials. Data collected from participants will include breathalyzer readings, urine and saliva drug screens, urine biomarkers (e.g., riboflavin), blood chemistries, plasma biomarkers, structural and neurochemical MRI brain images, cognitive testing results, and interviews and self-reports regarding substance use, psychiatric diagnoses, concomitant medications, and adverse events. To ensure confidentiality, all participant data will be number-coded, and only the investigators will have access to the master list of codes.

c. Compensation. To maximize participant retention, contingency management will be applied to participant compensation such that participants will be compensated significantly more for each subsequent MRI visit they attend (i.e., scan 1 = \$100, scan 2 = \$150), and participants will be given an additional \$50 bonus for completing both MRI visits. Participant compensation will be cash. Participants will be compensated \$50 for the initial psychiatric and medical evaluation appointment. Finally, participants will be compensated \$25 for each additional non-MRI appointment (i.e., 2 total). Compensation will thus be \$400 per participant. In our experience, this level of compensation is fair for the time commitment required without unduly coercing participants to enroll in the study despite potential concerns.

d. Potential Risks

1. Loss of Confidentiality. Individuals will be asked questions about their psychiatric symptoms. This information is highly confidential and all attempts will be made to safeguard privacy and confidentiality.
2. Medication side effects. NAC has a generally benign adverse effect profile. A meta-analysis of studies evaluating long-term oral treatment with NAC for prevention of chronic bronchitis found that NAC was well tolerated, with generally mild, most commonly gastrointestinal adverse effects that did not require treatment interruption (Grandjean et al., 2000). Common adverse effects of NAC include dry mouth, nausea, vomiting, and diarrhea. The proposed study will carefully monitor potential medication-related risks via weekly

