scheduled visits and assessment of adverse events (including assessment of suicidal ideation and behavior at each and every study visit). The study physician, [name] (Co-I), will determine if the participant should be discontinued from the medication due to adverse drug reactions and will treat clinically as needed. Any confirmed incidence of serious adverse events that are deemed probably or definitely due to the study medication will result in immediate discontinuation of the study medication and follow-up assessments will be conducted until resolution. Subjects will be referred for treatment as necessary.

3. Drug interactions. Due to potential interactions with NAC, participants may not take nitroglycerin or carbamazepine at any time during participation in the study. As noted earlier, BD participants will be required to be taking a stable pre-existing regimen of at least one FDA-approved mood stabilizing medication treatment for BD. There are no known drug interactions with NAC and non-carbamazepine mood-stabilizing medications (i.e., lithium, lamotrigine, divalproex sodium, 2nd generation antipsychotic).
4. Unknown Medication Risks. While NAC is approved by the FDA, it is not approved for the use in this study (i.e. the treatment of Bipolar Disorder). Because of this, there may be unknown medication side effects. Study clinicians and the study physician will monitor all adverse events throughout the study as well as the likelihood that they are related to the study medication. In the event that there are any serious adverse events, the study physician will instruct the participant to discontinue the use of the study medication.

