6. Mood destabilization. Exacerbation of depressive or manic symptoms during the course of the study is a risk for BD subjects regardless of treatment condition. We will minimize this risk by assessing mood symptoms, including suicidal ideation and behavior, at each and every study visit. Assessment of suicidal ideation will be conducted using primarily the Columbia-Suicide Severity Rating Scale (C-SSRS) and also the MADRS. Any participant who answers affirmatively to item 4 (SI with some intention of acting on them) or item 5 (SI with plan) on the C-SSRS or scoring > 4 on item 4 of the MADRS will be immediately removed from the study and procedures for emergent clinical assessment begun (see 2.c. below, *Protection Against Risk*). Participants experiencing sufficient deterioration of mood stability to result in clinically significant impairment in functional capacity will be appropriately referred. Any subject exhibiting mood destabilization that is sufficient to pose an imminent danger to self or others will be accompanied by the study physician to the University Hospital Emergency Department for immediate assessment for psychiatric hospitalization.
7. Pregnancy. MRI is used in this study. Participants who are pregnant or are trying to become pregnant should not participate as to ensure there is no risk to an embryo or fetus. Pregnancy tests will be conducted to ensure participants are not pregnant during study procedures.

2. Adequacy of Protection Against Risks

a. Recruitment and Informed Consent. Recruitment will occur by clinical referral and response to advertisements. IRB-approved study staff with advanced clinical degrees (e.g., PhD, MD) will obtain informed consent. Interested individuals will be given a brief description of the study and if still interested will be scheduled for a screening visit. At the screening visit, potential participants will be provided a copy of the IRB-approved consent document to review. After providing the participant with time to read the consent, IRB-approved study

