staff will review the consent document page by page with the participant and answer any questions. Only then will the participant be asked to sign the consent document. Participants will be given a copy of the signed consent document. The entire informed consent process will be documented in the research progress notes. The signed, original consent document will be maintained in the participant source record with a copy of the consent binder located at the Institute of Psychiatry, Department of Psychiatry and Behavioral Sciences, Medical University of South Carolina.

b. Safety Assessments. At every visit, IRB-approved study staff with advanced clinical degrees (e.g., PhD, MD) will clinically evaluate subjects' manic and/or depressive symptoms, including suicidal ideation. Mood symptoms will also be quantified using standardized instruments including C-SSRS, MADRS, YMRS, BDI-II, and BAI. Adverse events will be assessed at every study visit.

c. Protection Against Risk. Psychiatric Risks. The investigative team has a great deal of experience working with the study population and has the resources to make appropriate referrals as needed. Psychiatric symptoms will be assessed on a weekly basis by standardized assessments and by clinical interview. Participants answering affirmatively to item 4 (SI with some intention of acting on them) or item 5 (SI with plan) on the C-SSRS or scoring >4 on the suicide item (item 4) of the MADRS, or otherwise exhibiting potentially life-threatening decompensation in mood or other psychiatric symptoms at any study visit will be removed from the study and procedures for emergent clinical assessment begun at once. Briefly, actively suicidal participants will be accompanied to the adult ER in the main MUSC hospital by the study psychiatrist ([name], co-I). One-to-one accompaniment and supervision by the study psychiatrist will continue until the participant is admitted for triage in the ER. Should a participant refuse voluntary assessment in the ER, MUSC Public Safety will be called immediately and involuntary commitment papers will be filled out by [name]; participants refusing voluntary assessment will be accompanied at all times by study personnel and not allowed to leave the research clinic during emergency procedures. While a rare event, over the past 15 years [name] has implemented these procedures successfully 10-12 times and study participants have been admitted to the Institute of Psychiatry without exception.

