Medical Risks. NAC is largely excreted by a hepatic route. A blood chemistry panel will be performed and reviewed by the study physician prior to beginning the study medication. Participants with clinically significant hepatic (transaminases elevated > 3 times normal) insufficiency will not be eligible to participate in the study. Subjects will be referred for treatment as necessary.

MRI Risks. The investigative team has a great deal of experience with human MRI research and [name] is a core faculty member of the CBI at MUSC. MRI safety and comfort will be assessed at baseline and at each MRI visit. Participants with non-MRI-safe medical implants or ferrous objects will be excluded from participation as will individuals evidencing significant discomfort with MRI.

Pregnancy. NAC is rated as a *Category B* medication in terms of pregnancy. Because there are no adequate controlled studies of NAC in pregnant women, it is unknown whether the drug can cause fetal harm or affect reproductive capacity in humans. Therefore, women of childbearing potential must agree to pregnancy testing and use of adequate contraception in order to be eligible to participate in the study. Females will be given a urinary pregnancy test at the screening visit and weekly thereafter. Any female participant who becomes pregnant during the study will be discontinued from the study medication and removed from study participation. For all included females of childbearing potential, current forms of birth control and date of last menstruation will be assessed at each study visit.

Confidentiality. Records with identifying information (e.g., consent documents) will be stored in a locked file. All other non-MRI participant data will be collected via direct data capture (REDCap); MRI data will be automatically transferred to Linux-based servers managed by CBI. Both MRI and non-MRI data will be stored in restricted access directories on password-protected, encrypted servers managed by CBI and the Department of Psychiatry and Behavioral Sciences at MUSC. Participants will be given an ID number for all MRI and non-MRI data files. The master list of codes will be accessible only to the investigators, and will be stored in a locked office.

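### The human-subjects section states weekly visits, psychiatric assessments and pregnancy tests, but the schedule has five visits about two weeks apart after Visit 2 and no pregnancy test at either dispensing visit

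*Combined protocol and SAP*

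**What the plan says.** Protection of Human Subjects makes three statements of weekly frequency.

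- **Visits and adverse events** (1.d.2, one sentence broken across a page): "The proposed study will carefully monitor potential medication-related risks via weekly" and then "scheduled visits and assessment of adverse events (including assessment of suicidal ideation and behavior at each and every study visit".
- **Psychiatric symptoms** (2.c, Psychiatric Risks): "Psychiatric symptoms will be assessed on a weekly basis by standardized assessments and by clinical interview".
- **Pregnancy** (2.c, Pregnancy): "Females will be given a urinary pregnancy test at the screening visit and weekly thereafter". The same paragraph adds the rule "Any female participant who becomes pregnant during the study will be discontinued from the study medication and removed from study participation".

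The research plan describes a different schedule. C.1 gives each condition two visits, on Day 1 (dispensing) and Day 14 (MRI). C.3.c puts a 14-day washout between conditions. Table 2 lists Visits 1 to 5 (V1 to V5) and nothing else. Its pregnancy-test row is marked at V1, V3 and V5; dispensing is at V2 and V4. C.3.b, which describes V2 and V4, lists mood ratings, substance-use history and a urine drug screen, but no pregnancy test. On the end of dosing, C.3.c says "Participants will take their final medication dose in front of staff, 1 hour before MRI, to ensure compliance" and "Participants will discontinue study medication following each MRI".

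**The concern.** The two parts of the document cannot both be followed. Staff who keep to Table 2 depart from what section 2.c says about protection. The text matters because participants must be in a mood episode or only partly remitted from one, and 1.d.6 names worsening of mood as a risk in either condition.

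The pregnancy part goes beyond wording. Section 2.c says that fetal harm from N-acetylcysteine is unknown and gives this as the reason for testing and contraception. Yet at both visits where a course starts, with a first 1.5 g dose (or placebo) taken in front of staff, no test is scheduled. Both tests after screening come when the course is ending. By testing alone, the rule to stop medication in a pregnant participant can therefore act only at the end of a course or, after V3, by preventing the second one.

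**Working it through.** **Inputs.** Day 1 and Day 14 visits in each condition (C.1); 14-day washout (C.3.c); five visits, with pregnancy tests at V1, V3 and V5 and dispensing at V2 and V4 (Table 2); 12 participants (C.2); payments (1.c). The V1 to V2 interval is not stated.

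**Check that there are only five visits.** Initial evaluation $50, two other non-MRI appointments at $25, scans at $100 and $150, and a $50 completion bonus: 50 + 2 × 25 + 100 + 150 + 50 = $400. This reproduces the stated total, so no further paid visit exists. The only contact described between visits is the daily actigraphy log sent by text or e-mail (C.3.b), which is neither a clinical interview nor a urine test.

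**Visit gaps.** Take V2 as Day 1 and V3 as Day 14. V4 depends on how the washout is counted, and V5 = V4 + 13.

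| Counting of washout | V2, V3, V4, V5 (day) | Gaps (days) | V3 to V5 |
|---|---|---|---|
| V4 is 14 days after V3 | 1, 14, 28, 41 | 13, 14, 13 | 27 |
| 14 full days between V3 and V4 | 1, 14, 29, 42 | 13, 15, 13 | 28 |

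No gap is 7 days. The ratio to a weekly interval is 13/7 = 1.9 to 15/7 = 2.1. Weekly contacts from V2 would fall on Days 1, 8, 15, 22, 29 and 36, which is six; the plan has four visits from V2 on.

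**Pregnancy tests after screening.** If V1 is k days before V2, weekly testing gives floor((V5 day − 1 + k)/7) tests by V5. With V5 on Day 41 or 42:

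- k = 0: floor(40/7) or floor(41/7) = 5
- k = 7: floor(47/7) or floor(48/7) = 6
- k = 14: floor(54/7) or floor(55/7) = 7

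Table 2 gives 2. The range of k from 0 to 14 days is an assumption.

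**Age of the last test at dispensing.** At V4 it is 14 to 15 days (from V3). At V2 it equals the unstated V1 to V2 interval.

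**What Table 2 confirms at every visit.** The YMRS, MADRS, HAM-A and C-SSRS row is marked at all five visits. There is no row for adverse events or for the contraception and menstruation review; these are set for every visit by text only (1.d.2, 2.b, 2.c). Section 2.b names BDI-II and BAI among the instruments in its every-visit paragraph, but Table 2 marks them at V1, V3 and V5 only.

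**The case against.** The strongest case on the other side is that the operational sections agree with one another on visit timing, so staff can run the study from them and the error is one loose word used three times. Mood, C-SSRS, adverse-event and contraception reviews are set for every visit, and the suicidality removal rule can act at any of them. Between visits, 2.c (Emergencies) provides a 24-hour on-call system, clinicians by pager and emergency unblinding. Current suicidal or homicidal ideation, MADRS above 35 and YMRS above 25 are excluded, and a daily mood stabilizer is required. For pregnancy, adequate contraception is required and reviewed at each visit, V2 and V4 included, the drug is rated Category B, and the V3 and V5 tests serve the purpose given in 1.d.7: "Pregnancy tests will be conducted to ensure participants are not pregnant during study procedures". Weekly psychiatric assessment could also be met by contacts outside Table 2.

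Most of this stands, and it limits the harm. It does not remove the conflict: no such contacts are planned, and a urine test cannot be done by telephone. On-call cover responds to events; it is not scheduled assessment. It is also fair that tests at V2 and V4 would not make testing weekly, so they are a recommendation in their own right and the wording must change regardless.

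A reader might infer more than the documents support:

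- *That women are dosed without any prior test.* They are not. The V1 test precedes V2 and the V3 test precedes V4. What is missing is a test at the dispensing visit itself.
- *That mood and suicidality go unmonitored.* They are rated at all five visits; only the weekly frequency is unmet.
- *That the trial's result is at risk.* Nothing here enters the glutathione model or the sample size.

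**Conclusion.** The inconsistency is real and should be fixed, at modest weight. Three weekly statements in participant-safety text are not met by a schedule whose gaps after V2 are 13, 14 to 15 and 13 days, so the stated frequency is about twice the scheduled one. After screening there are 2 pregnancy tests, where weekly testing would give 5 to 7. Neither dispensing visit has one, and the longest interval between tests after V2 is 27 to 28 days, about half of it drug-free.

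The gaps rest only on the stated visit days and the two ways of counting the washout. The 5 to 7 range also rests on the assumed 0 to 14 days between V1 and V2. Table 2 supports every-visit assessment for the four clinician ratings only; adverse events and contraception rest on text alone.

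**What to change.** 1. In 1.d.2 and in 2.c (Psychiatric Risks), replace the weekly wording with *at every study visit (about every two weeks)*.
2. Add a urine pregnancy test before dispensing at V2 and V4 to Table 2 and C.3.b. Urine is already collected there for the drug screen. Change 2.c (Pregnancy) to *at every study visit (V1-V5)*. The longest test interval after V2 falls from 27-28 days to 14-15.

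**Cost.** A short amendment with no new visits. At most 2 × 12 = 24 extra urine tests, even if all 12 participants were women of childbearing potential. The stated monitoring frequency becomes less favourable, and the amendment should say so.

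Only if the sponsor really intends weekly monitoring should interim contacts be added to Table 2 in place of change 1. Keeping every gap after V2 to 7 days or less takes the sum of (ceil(gap/7) − 1): 1 + 1 + 1 = 3 or 1 + 2 + 1 = 4 contacts per participant, so 36 to 48 for 12 participants. Remote contacts would not supply urine tests, so the pregnancy wording would still need correcting.
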